^s Treatments that have been administered within the 7 days prior to the date of signing the ICF or during the Screening phase will be recorded in the eCRF. All medications and significant non-drug therapies administered after the first dose of test article must be recorded in the eCRF (see [Section 13](#)).

^t Up to 4 samples will be collected per subject between study Days 1 to 7. The PK sample collection schedule for the individual subject will be provided by the sponsor (see [Section 19](#)).

^u At any time after the first 3 days of iv treatment (after 4 iv doses) the subject may be switched to po medication based upon determination of clinical stability. Refer to protocol [Section 14.3.1.2](#) for required criteria to switch to po treatment. The first po dose should be administered in the morning, 12-24 hours after the last iv dose. At the investigator's discretion, all therapy may be discontinued after the seventh day of treatment, when the infection is considered clinically cured (based on normalization of the clinical signs and symptoms of infection and the investigator's clinical assessment that continued systemic antibacterial therapy is no longer needed).

^v If bacteria are isolated from baseline blood cultures, repeat blood cultures should be collected on the day that the positive blood culture is detected. If subsequent blood cultures are also positive, repeat the blood cultures as necessary until negative blood cultures are obtained. (see [Section 16.1.4.3](#))

^w Culture and Gram stain from an adequate quality sputum specimen or other respiratory specimen. At the EOT and/or PTE visit, respiratory specimen cultures and Gram stains should be obtained only for subjects who are Clinical Failures and require alternative antibacterial treatment for CABP (see [Section 17.2.2.1](#)).

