17.2.2 Microbiological Assessments

17.2.2.1 Respiratory Culture and Gram Stain

At the Screening visit collection of an adequate quality expectorated or induced sputum or other respiratory specimen reflecting fluid from the lower respiratory tract (eg, respiratory fluid obtained by bronchoalveolar lavage or bronchoscopy; pleural fluid obtained by thoracentesis; or expectorated or induced sputum meeting adequacy criteria) should be attempted from all subjects and submitted to the local microbiology laboratory for Gram stain and culture (see [STUDY FLOWCHART](#)). The date, time and type of specimen submitted will be recorded on source documents at the local laboratory. These specimens may be obtained as part of routine, non-study evaluation of a subject being evaluated for CABP and therefore could be obtained prior to obtaining informed consent.

An adequate quality sputum specimen will be defined as having the following 2 findings as reported by the local laboratory:

1. < 10 Squamous epithelial cells/low power field (lpf) (ie, 100 \times)
2. > 25 Polymorphonuclear cells/lpf (ie, 100 \times)

Adequate quality sputum specimens and other Screening respiratory specimens for culture should be obtained prior to first dose of test article. In the event that a sputum specimen is determined to be inadequate, or cannot be obtained prior to the first dose of test article, collection of a specimen should be attempted within 24 hours after the first dose of test article. As the infection responds to therapy, obtaining repeated specimens for culture or examination may not be clinically appropriate and/or there may be no material for culture. At the EOT and/or PTE visit, respiratory specimen cultures and Gram stains should be obtained only for subjects who are Clinical Failures and require alternative antibacterial treatment for CABP.

All respiratory and blood specimens submitted to the local laboratory are to be processed for a Gram stain of the specimen and for aerobic culture. Laboratory reports on Gram stains should include a semi-quantitative description of the number of polymorphonuclear leukocytes per low power field (ie, 100 \times) and a description of bacteria seen. For Gram stains of respiratory

specimens a semi-quantitative description of the number of squamous epithelial cells per low power field (ie, 100 \times) should also be included.

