5.2.2 Secondary Efficacy Outcomes

5.2.2.1 Investigators Assessment of Clinical Response

The investigator will make an assessment of Clinical Response at the EOT and PTE Visits, based on the definitions below. The secondary efficacy outcome is the overall assessment of clinical response at PTE (derived from the investigator assessments at the EOT and PTE Visits) in the ITT and CE-PTE populations as defined in [Table 3](#).

EOT Visit

At the EOT Visit (on the calendar day of, or within 2 days following the last dose of test article), the investigator will indicate the clinical status of the infection under study as detailed below.

Clinical Success: the subject is alive and the infection is sufficiently resolved such that further antibacterial therapy is not needed. These subjects may have some residual findings related to infection (ie, cough) requiring ancillary (ie, non-antibiotic) treatment (eg, expectorant). In order for the subject to be considered a Clinical Success at EOT, the subject may not meet any criteria for Clinical Failure or Indeterminate at EOT.

Clinical Failure: the subject requires alternative antibacterial treatment for CABP prior to EOT related to either (a) progression or development of new symptoms to CABP or (b) development of infectious complications of CABP (eg, empyema, lung abscess) or (c) subject developed an AE that required discontinuation of study therapy prior to the EOT. Other reasons for clinical failure are:

- Subject is receiving antibacterial therapy that may be effective for the infection under study for a different infection from the one under study.
- Death prior to EOT.

Indeterminate: the clinical response to test article could not be adequately inferred due to:

- Subjects were not seen for EOT evaluation because they withdrew consent, were lost to follow-up, other reason (specify).
- Other specified reason.

PTE Visit

At the PTE Visit (5 to 10 days after the subject's last day of study therapy) the investigator will indicate one of the following outcomes relating to the primary infection under study:

Clinical Success: survival after completion of a test article regimen without receiving any systemic antibacterial therapy other than test article, resolution of signs and symptoms of the infection present at Screening with no new symptoms or complications attributable to CABP and no need for further antibacterial therapy.

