Clinical Failure: the subject requires alternative antibacterial treatment for CABP prior to PTE related to either (a) progression or development of new symptoms of CABP or (b) development of infectious complications of CABP (eg, empyema, lung abscess). Other reasons for clinical failure are:

- The subject is receiving antibiotics that may be effective for the infection under study for a different infection from the one under study.
- Death prior to PTE.

Indeterminate: the clinical response to test article could not be adequately inferred due to:

- Subjects were not seen for PTE evaluation because they withdrew consent, were lost to follow-up, other (specify).
- Other specified reason.

Overall Clinical Response at PTE (based on the investigator's assessment) is determined as follows from the investigator's assessments at the EOT and PTE Visits:

Table 3. Investigator's Assessment of Clinical Response

EOT Visit	PTE Visit	Overall Assessment of Clinical Response at PTE Visit
Success	Success	Success
Success	Failure	Failure
Success	Indeterminate	Indeterminate
Failure	Success	Failure
Failure	Failure	Failure
Failure	Indeterminate	Failure
Indeterminate	Success	Indeterminate
Indeterminate	Failure	Failure
Indeterminate	Indeterminate	Indeterminate

Abbreviations: EOT = end of treatment; PTE = post-therapy evaluation.

For the ITT population, the proportion of ITT subjects with a Clinical Success is defined using the following formula (where the denominator adds to the total number of subjects in the ITT population):

Number of subjects with Clinical Success

(Number of subjects with Clinical Success + Number of subjects with a Clinical Failure + Number of subjects with an Indeterminate response)

By definition, subjects in the CE-EOT and CE-PTE populations cannot have an Indeterminate response. Thus, for the CE-EOT and CE-PTE populations, the proportion of subjects with a Clinical Success is defined using the following formula:

Number of subjects with Clinical Success

(Number of subjects with Clinical Success + Number of subjects with a Clinical Failure)

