5.2.2.2 Microbiologic Outcomes

Microbiological response definitions for the evaluations performed at the EOT and PTE Visits and analyzed in the microITT and ME populations are presented in the table below. Post-baseline microbiological samples will be collected only as clinically indicated. Atypical pathogens identified only by acute and convalescent serology or baseline urinary antigen tests (UAT), and *Streptococcus pneumoniae* identified only by baseline UAT can only have a presumed or indeterminate microbiologic response.

If a subject has the same pathogen (ie, same genus and species) identified from both a respiratory and blood specimen, a microbiological response is determined for each of the pathogens. The microbiologic response for the respiratory pathogen is based on the pathogen isolated from the EOT or PTE specimen, if a specimen was collected. The microbiologic response for the blood pathogen is based on the blood sample collected at EOT or PTE, or if a sample was not collected at the post-baseline visit, the blood sample collected prior to and closest to the visit. For the pathogen specific microbiologic response, the worst outcome for the pathogen should be summarized. If *Streptococcus pneumoniae* is identified from both a UAT and a culture, the culture should be used to determine microbiological response.

Table 4. Per-Pathogen Microbiological Response Definitions at the EOT and PTE Visits

Term	Definition
Eradication	The baseline pathogen based on culture was absent from repeat culture(s) of the same sample type (blood or respiratory specimen).
Presumed Eradication	No post-baseline source specimen to culture in a subject assessed with a clinical success by the Investigator
Persistence	The baseline pathogen based on culture was present in repeat culture(s) of the same sample type (blood or respiratory specimen).
Presumed Persistence	No post-baseline source specimen to culture in a subject assessed with a clinical failure by the Investigator
Indeterminate	The subject's clinical response is indeterminate or other circumstance that precludes a microbiological evaluation

Abbreviations: EOT = end of treatment; PTE = post-therapy evaluation.

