Microbiological outcomes are further categorized as favorable, unfavorable, and indeterminate. Favorable microbiological outcomes are defined as eradication or presumed eradication. Unfavorable microbiological outcomes are defined as persistence or presumed persistence. Microbiological response will be derived using electronic microbiology data from the central laboratory and from pathogen determination provided by the Sponsor for each baseline isolate.

Overall microbiological response at PTE is determined as follows from the microbiological responses at the EOT and PTE Visits:

Table 5. Per-Pathogen Microbiologic Response

EOT Visit	PTE Visit	Overall Microbiologic Response at PTE
Favorable	Favorable	Favorable
Favorable	Unfavorable	Unfavorable
Favorable	Indeterminate	Indeterminate
Unfavorable	Favorable	Unfavorable
Unfavorable	Unfavorable	Unfavorable
Unfavorable	Indeterminate	Unfavorable
Indeterminate	Favorable	Indeterminate
Indeterminate	Unfavorable	Unfavorable
Indeterminate	Indeterminate	Indeterminate

Abbreviations: EOT = end of treatment; PTE = post-therapy evaluation.

Note: Favorable is defined as eradication or presumed eradication. Unfavorable is defined as persistence or presumed persistence.

Per-subject responses will be based on per-pathogen responses. To have an overall per-subject favorable microbiologic response, the outcome for each baseline pathogen must be favorable (eradicated or presumed eradicated). If the outcome for any pathogen is unfavorable (persistence or presumed persistence), the subject will be considered to have an unfavorable per-subject microbiologic response. Subjects with an indeterminate response for all pathogens will be considered to have an indeterminate per-subject microbiologic response. If the same pathogen is isolated from multiple sample types (blood, respiratory, urine), the worst outcome will be used to determine per-subject microbiologic response. Superinfections will not be considered in the microbiological response. Microbiological response from worst to best are as follows: persistence, presumed persistence, indeterminate, presumed eradication, and eradication.

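### SAP Table 4 can score a negative culture taken on rescue antibacterials as Eradication, so a rescued Clinical Failure may count as a favorable microbiological response

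*Combined protocol and SAP*

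**What the plan says.** **Who is cultured.** Protocol v2.0, section 17.2.2.1, says that EOT and PTE respiratory specimens should be "obtained only for subjects who are Clinical Failures and require alternative antibacterial treatment for CABP". Flowchart footnote w repeats this. SAP section 5.2.2.2 is looser: "Post-baseline microbiological samples will be collected only as clinically indicated".

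**When.** EOT is on the day of the last dose or up to 2 days later; PTE is 5 to 10 days after the last day of therapy. Failure at EOT is tied to a need arising earlier ("the subject requires alternative antibacterial treatment for CABP prior to EOT related to either" lack of effect, or an AE), and failure at PTE likewise ("the subject requires alternative antibacterial treatment for CABP prior to PTE").

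**How it is scored.** Table 4 of the SAP gives Eradication when "The baseline pathogen based on culture was absent from repeat culture(s) of the same sample type (blood or respiratory specimen". A failure with no specimen is Presumed Persistence; a success with no specimen is Presumed Eradication. "Favorable microbiological outcomes are defined as eradication or presumed eradication". Table 5 combines the EOT and PTE results.

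**Who stays in.** SAP section 6.1.4.3 removes subjects given active concomitant antibiotics from the CE sets, except those treated for insufficient effect of the test article. The ME sets are the overlap of CE and microITT (section 6.1.5).

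**The concern.** A negative culture in a subject already taking another effective antibacterial does not show that the test article cleared the pathogen. Table 4 nevertheless counts it as favorable for the assigned arm. Under the protocol schedule the only follow-up respiratory cultures come from subjects who need such a drug, and nothing in the documents puts the specimen before its first dose.

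The scheduled cultures also act in one direction. An uncultured failure is already Unfavorable and an uncultured success already Favorable. A scheduled culture in a failure can therefore only leave the result Unfavorable or turn it Favorable. A negative culture taken before rescue may be a genuine finding; one taken on rescue cannot be told apart from the rescue drug's effect.

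At stake are the per-subject and per-pathogen favorable rates in the microITT and ME sets, the confidence interval for the per-subject difference, and the concordance table of clinical against microbiological response (SAP section 10.4). Presumed outcomes copy the clinical result, so for respiratory pathogens any discordance produced by the scheduled cultures falls in the failure/Favorable cell, which is the cell exposed here.

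**Working it through.** No stated figure is in dispute, so the check is a trace of the rules for a subject with one culture-identified respiratory pathogen.

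| EOT | EOT score | PTE | PTE score | Overall at PTE (Table 5) |
|---|---|---|---|---|
| Failure, no specimen | Presumed Persistence | Failure, negative on rescue | Eradication | Unfavorable |
| (a) Failure, negative on rescue | Eradication: Favorable at EOT | Failure, negative on rescue | Eradication | Favorable |
| (a) Failure, negative on rescue | Eradication: Favorable at EOT | Failure, no PTE specimen | Presumed Persistence, if Table 4 is read visit by visit | Unfavorable |
| (b) Success, no specimen | Presumed Eradication | Failure, negative on rescue | Eradication | Favorable |
| Success, no specimen | Presumed Eradication | Failure, no specimen | Presumed Persistence | Unfavorable |

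The last two rows have the same clinical course and differ only in whether a culture was taken. Path (a) reaches the EOT result in every case. Path (b) reaches the overall PTE result.

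Limits on who can be affected:
- SAP section 5.2.2.2 allows only presumed or indeterminate responses for atypical pathogens identified only by serology or urinary antigen, and for *S. pneumoniae* identified only by urinary antigen.
- A favorable per-subject result needs every baseline pathogen to be favorable, and the worst outcome across sample types is used.
- Subjects who die count as failures but may never be cultured.
- Blood cultures follow their own repeat rule (Protocol section 16.1.4.3).

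**Scale.** The plan's microITT size reproduces: 0.27 × 750 = 202.5, stated as 202. With equal arms that is 101 each, so one reclassified subject moves an arm's rate by 1/101 = 0.99 points.

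**Illustration at EOT (assumptions, not an estimate).** Let *c* be the share of microITT with culture-based pathogens only, *q* the clinical failure rate and *f* the share of those failures with a negative culture on rescue. The favorable rate rises by *c* × *q* × *f*. Take *q* = 0.20, borrowed from the 80% early-response rate that SAP Table 1 assumes for microITT. Let *f* run from 0.025 (10% cultured on rescue × 25% negative) to 0.25 (50% × 50%).
- *c* = 1: 0.20 × 0.025 = 0.5 points, to 0.20 × 0.25 = 5.0 points.
- *c* = 0.5: 0.25 to 2.5 points.

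With the same *c* and *f* in both arms, a true difference *d* shrinks to *d*(1 − *cf*). For *d* = −10 points and *c* = 1 that is −9.75 to −7.5; for *c* = 0.5 it is −9.9 to −8.75. The documents supply neither *c* nor *f*.

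**The case against.** The strongest reply is that the plan already limits the damage. Table 5 carries an Unfavorable EOT result forward, so an uncultured EOT failure cannot be turned Favorable by a later negative culture. The decision to stop test article prompts the EOT evaluation (Protocol sections 14.3.1.1.1 and 14.3.1.3.1), and needing another antibacterial means that test article stops (section 13.1). EOT is therefore tied to the switch, and sampling after rescue has begun is possible but not shown to be usual. Both points stand; they narrow the reach to paths (a) and (b).

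A second reply is that Table 4's Indeterminate row has a residual clause for circumstances that prevent a microbiological evaluation, and that the laboratory manual or the Evaluability Review Team's process document may set a timing rule. Those documents are not in the file, so this cannot be excluded. Nothing visible applies the clause to rescue therapy. SAP section 8.3, in its item on missing specimens, reserves Indeterminate for subjects whose clinical response is Indeterminate, and these subjects are failures. Section 6.2.2 gives the review team pathogen determination, not Table 4 scoring.

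A reader might also infer that the PTE culture has lost its purpose. That does not follow. The amendment rationale lists persistence, resistant pathogens and new pathogens, and a culture on rescue can still show each of them. What it cannot do is rule persistence out.

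**Conclusion.** The gap is real on the text. Table 4 lets a negative culture obtained on rescue therapy count as Favorable for the assigned arm, through paths (a) and (b) only. The direction, toward a higher favorable rate and, if both arms are affected alike, a smaller difference, follows from the rules. The size cannot be derived, because the documents do not say how many failures are cultured, when, or with what result.

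Three stronger readings are tempting, and the documents do not support them.
- **PTE results are broadly inflated because PTE falls days after rescue.** Table 5 blocks this for anyone already Unfavorable at EOT.
- **The inflation is a known number of points across all 202 microITT subjects.** Subjects identified only by serology or urinary antigen cannot be scored Eradication, and no culture rates are given.
- **All rescued subjects stay in CE and ME.** Only those rescued for insufficient effect do; subjects given active drugs after an AE-driven stop or for another infection are excluded.

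The primary and secondary clinical endpoints are untouched. SAP section 5.2.2 defines microbiological response among the secondary outcomes, but section 10.4 analyses it as supportive, with descriptive intervals and no non-inferiority conclusion. This is a scoring rule to correct, not a threat to the main result.

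**What to change.** Amend SAP Table 4 before unblinding:
- A culture collected after the first dose of a non-study systemic antibacterial potentially effective against the baseline pathogen may establish Persistence but not Eradication.
- If there is no earlier post-baseline culture, the response follows the investigator's clinical outcome, that is, Presumed Persistence in a Clinical Failure.
- Report Table 4 scoring as now written as a sensitivity analysis.
- Keep the planned concordance table, using the amended scoring. Limiting it to subjects cultured before rescue would remove nearly all clinical successes, who are not scheduled for culture.

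Cost: SAP wording and a comparison of specimen time with antibiotic start time. Antibiotic start times are already collected, and missing ones are queried (SAP section 8.3). The judgement of potential effectiveness resembles the one section 6.1.4.3 already requires for the CE sets, extended to microITT. The change concerns scoring only, not when or how subjects are treated.

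Downside: the favorable rate may be slightly lower, and some true eradication may be scored Presumed Persistence, for example after an AE-driven switch in microITT. The sensitivity analysis shows how much depends on this.

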Superinfection	Isolation of a non-baseline pathogen from blood or respiratory cultures while the subject is on test article and the subject shows progression or development of new symptoms of CABP or development of infectious complications of CABP (ie, the subject is deemed a clinical failure by the investigator at the EOT Visit)
New infection	Isolation of a non-baseline pathogen from a post-treatment culture of a blood or respiratory specimen and the subject shows progression or development of new symptoms of CABP or development of infectious complications of CABP (ie, the subject is deemed a clinical failure by the investigator at the PTE Visit)

Abbreviations: CABP = community-acquired bacterial pneumonia.

For subjects with multiple microbiological samples taken either while the subject is on test article (for determination of superinfection) or post-treatment (for determination of new infection) all cultures will be used in the analysis.

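### SAP Table 4 can score a clinical failure as Eradication when the baseline pathogen regrows from the other sample type, and no response, superinfection or new-infection table counts that regrowth

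*Combined protocol and SAP*

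**What the plan says.** SAP section 5.2.2.2, Table 4, assigns a response to each baseline pathogen at EOT and PTE.

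- Persistence: "The baseline pathogen based on culture was present in repeat culture(s) of the same sample type (blood or respiratory specimen".
- Eradication: "The baseline pathogen based on culture was absent from repeat culture(s) of the same sample type (blood or respiratory specimen". It carries no condition on clinical outcome or on any other culture.
- Presumed Persistence: "No post-baseline source specimen to culture in a subject assessed with a clinical failure by the Investigator".

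The SAP then states: "Favorable microbiological outcomes are defined as eradication or presumed eradication".

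Table 6 adds two categories for later isolates, both for clinical failures. Superinfection starts from "Isolation of a non-baseline pathogen from blood or respiratory cultures while the subject is on test article", and new infection from "Isolation of a non-baseline pathogen from a post-treatment culture of a blood or respiratory specimen". Neither admits an organism that was already a baseline pathogen.

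Two rules combine sources. The pathogen-specific response takes the worst outcome when the same genus and species comes from both blood and a respiratory specimen. For the per-subject response: "If the same pathogen is isolated from multiple sample types (blood, respiratory, urine), the worst outcome will be used to determine per-subject microbiologic response".

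The specimens come from Protocol Version 2.0. Section 16.1.4.3 repeats blood cultures after a positive baseline culture until they turn negative. Under section 17.2.2.1, at EOT and PTE, "respiratory specimen cultures and Gram stains should be obtained only for subjects who are Clinical Failures" who also need other antibacterial treatment.

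**The concern.** The definitions look only at the source that was positive at baseline, and the later-isolate categories look only at new organisms. The baseline organism appearing in a source that was not positive at baseline falls between them.

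If the baseline source has been recultured and is negative, the rule returns Eradication. A subject who failed clinically, and from whom the baseline species has just been grown, is then reported as a microbiological success.

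At stake are the per-subject and per-pathogen favorable rates in the microITT and ME populations (SAP section 10.4). The protocol's summary of changes says the PTE respiratory culture was added partly to find out whether infection at that visit reflects persistence of the first pathogen. For a pathogen found only in blood at baseline, Table 4 does not use that culture.

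**Working it through.** The plan attaches no figure to this rule, so the check is to run the definitions through every case.

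**1. Enumeration.** Take a clinical failure with one cultured baseline pathogen from one source. There are 2 baseline sources (respiratory, blood), 3 results for the repeat culture of that source (none, negative, positive) and 3 for the other source: 2 × 3 × 3 = 18 cases. Both baseline sources give the same pattern:

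| Repeat culture, baseline source | Other source: none or negative | Other source grows the baseline species |
|---|---|---|
| None | Presumed Persistence (unfavorable) | Presumed Persistence (unfavorable) |
| Negative | Eradication (favorable) | **Eradication (favorable)** |
| Positive | Persistence (unfavorable) | Persistence (unfavorable) |

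The bold cell holds 2 of the 18 cases: (a) respiratory at baseline, later respiratory negative and blood positive; (b) blood at baseline, later blood negative and respiratory positive. Table 6 gives neither a category, because the organism is a baseline pathogen.

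**2. Could another rule catch them?**

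- The worst-outcome rules choose among responses already assigned. Table 4 assigns none to a source that was not positive at baseline.
- Presumed Persistence needs the source specimen to be missing. Here it exists.
- Indeterminate needs an indeterminate clinical response or something that prevents evaluation. The clinical response is Failure and a valid culture exists. SAP section 8.3, on missing specimens, also reserves Indeterminate for an indeterminate clinical response.
- The Evaluability Review Team (SAP section 6.2.2) decides whether an isolate is a pathogen. It does not override the response derivation.

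**3. Can they occur?** Case (b) follows from the schedule: blood is recultured until negative, and the specimen scheduled at a failure visit is respiratory. Case (a) needs a clinically indicated blood culture that turns positive alongside a negative repeat respiratory culture.

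**4. Carrying through to PTE (SAP Table 5).** In case (a) the EOT response is favorable. A subject given rescue antibiotics cannot be a Clinical Success at PTE. With no PTE respiratory specimen, the PTE response is Presumed Persistence if the investigator records Failure, or Indeterminate if clinical response is Indeterminate. Table 5 then gives unfavorable or indeterminate overall, so the overall result stays favorable only if a PTE respiratory culture is also negative. In case (b) a negative blood culture at the visit gives Eradication directly. Otherwise the result depends on section 5.2.2.2's rule that the closest earlier blood sample stands in. That rule is written in the paragraph on pathogens found in both sources; if it also covers blood-only pathogens, the cleared culture counts at EOT and PTE and the overall result is favorable.

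**5. Consistency.** Take two failures with identical follow-up: blood negative, sputum growing the baseline species. If baseline sputum was also positive, the worst-outcome rule gives Persistence. If baseline sputum was inadequate or unobtainable, Table 4 gives Eradication. Only the baseline specimen differs.

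**6. Size.** SAP section 5.1.1 expects 27% of 750 in microITT: 0.27 × 750 = 202.5, stated as 202. Per arm, 202 / 2 = 101. One reclassified subject moves the per-subject favorable rate by 1/101 = 0.99 percentage points. In a pathogen row of 5 to 10 subjects per arm (my assumption; no row sizes are given), one subject is 1/10 to 1/5, or 10 to 20 points.

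**The case against.** The strongest reply is that this is a rare event in a supportive analysis, and that the plan keeps it in view. Much of that stands.

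- A reader might infer that the regrowth is counted nowhere. It is not hidden. SAP section 9.2.1 lists every baseline and post-baseline isolate with specimen type. The subject stays a clinical failure. If the favorable result holds at PTE, the clinical-by-microbiological concordance analysis in section 10.4 shows a discordant subject. A fourfold MIC rise would enter the decreasing-susceptibility table. The gap is confined to the response, superinfection and new-infection tabulations.
- A reader might infer that any regrowth from the other source is scored favorable. It is not. Without a repeat culture of the baseline source, the failure is Presumed Persistence, already unfavorable; only the label differs.
- A reader might infer bias toward omadacycline or toward non-inferiority. Within an arm the error can only raise the favorable rate, but the same rule applies to both blinded arms. The documents show no direction for the treatment difference.
- Redefining Persistence in Table 4 itself as growth from any source would do harm. It would label a cleared bacteremia as persistent in the separate blood-pathogen summary of section 10.4. A blanket requirement for adequate sputum would also clash with section 6.1.3, which accepts Legionella from sputum whatever the Gram stain shows.

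The reply does not dispose of the rule itself. In the two cases identified it returns a favorable result that contradicts a culture in hand, and no listed safeguard changes that result.

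**Conclusion.** The point holds in a limited form and is worth correcting. Favorable scoring requires three things together: clinical failure, a negative repeat culture from the baseline source, and the baseline species from the other source. The blood-only case is the clearest. It rests on a negative blood culture at the visit, or on reading the closest-earlier-blood rule as covering blood-only pathogens. The respiratory-baseline case is mainly an EOT effect.

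Few subjects are likely and the documents give no frequency. The effect is about 1 percentage point per subject in the per-subject microITT rate, and more in small pathogen rows. Section 10.4 treats the microbiological results as supportive, with descriptive intervals and no non-inferiority conclusion. Early Clinical Response and the investigator's clinical response are unaffected.

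**What to change.** Leave the source-specific responses in Table 4 and the separate blood-pathogen summary unchanged. Add one rule to SAP section 5.2.2.2 for the pathogen-specific (worst-outcome) and per-subject responses, for example:

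*For a pathogen identified by culture at baseline, recovery of the same genus and species from the blood or respiratory culture used for that visit counts as Persistence, even if that sample type was not positive at baseline. The culture must qualify under the pathogen rules in section 6.1.3. Where no blood was drawn at the visit, the closest earlier post-baseline blood sample is used.*

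Restricting this to pathogens identified by culture preserves the existing rule that pathogens found only by antigen test or serology can have only presumed or indeterminate responses.

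Also report, by arm, the number of subjects whose baseline pathogen is recovered from a new sample type at any time after baseline. This picks up a positive blood culture between visits, which the visit-based response could miss.

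The cost is one added rule, one count and a small change to the derivation, using cultures already collected. The favorable rate may fall slightly.
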